6.5. Dose Modification

Dose modifications may occur in 1 of 3 ways:

- Within a cycle: dosing interruption until adequate recovery and dose reduction, if required, during a given treatment cycle;
- Between cycles: next cycle administration may be delayed due to persisting toxicity when a new cycle is due to start;
- In the next cycle: dose reduction may be required in a subsequent cycle based on toxicity experienced in the previous cycle.

The decision to proceed to the next dose level of PF-07265028 (either an increase or a decrease) will be made by the study team and the investigators based on safety, tolerability, and preliminary PK and/or pharmacodynamics data obtained in all participants at the prior dose level.

The dosing schedule may also be adjusted to expand a dosing cohort to further evaluate safety, PK, and/or pharmacodynamics findings at a given dose level or to add cohorts to evaluate additional dose levels. The study procedures for these additional participant(s)/cohort(s) will be the same as that described for other study participants/cohorts.

Every effort should be made to administer study intervention on the planned dose and schedule. In the event of significant toxicity, dosing of PF-07265028 may be delayed and/or reduced as described below. In the event of multiple toxicities, dose modification should be based on the worst toxicity observed and attribution for the combination treatment (for combination therapy). Participants are to be instructed to notify investigators at the first occurrence of any adverse symptom. In addition to dose modifications, investigators are encouraged to employ best supportive care according to local institutional clinical practices.

Toxicities potentially related to PF-07265028 should be managed according to the dose modifications described in Table 8.

Table 8. Dose Modifications for PF-07265028-Related Toxicity

Toxicity	Grade 1	Grade 2	Grade 3	Grade 4
Nonhematologic	Continue at the same dose level.	Continue at the same dose level.	Withhold dose until toxicity is Grade ≤ 1 , or has returned to baseline, then resume treatment at the same dose level or reduce the dose by 1 level at the discretion of the investigator.	Withhold dose until toxicity is Grade ≤ 1 , or has returned to baseline, then reduce the dose by 1 level and resume treatment, or discontinue at the discretion of the investigator.

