Hematologic	Continue at the same dose level.	Continue at the same dose level.	Withhold dose until toxicity is Grade ≤ 2 , or has returned to baseline, then resume treatment at the same dose level.	Withhold dose until toxicity is Grade ≤ 2 , or has returned to baseline, then reduce the dose by 1 level and resume treatment or discontinue at the discretion of the investigator.

Specific GI toxicities potentially related to PF-07265028 should be managed according to the dose modifications described in [Table 9](#).

090177e198aafefApproved\Approved On: 22-Nov-2021 20:52 (GMT)

Table 9. Dose Modifications for PF-07265028 Related GI Toxicity

Grade 1	Grade 2	Grade 3*	Grade 4
Continue at the same dose level and, institute standard of care supportive measures at the discretion of the investigator.	Continue at the same dose level and institute standard of care supportive measures at the discretion of the investigator. If recurrent and intolerable, withhold dose until toxicity is Grade ≤ 1 , or has returned to baseline, then resume treatment at the next lower dose level	Withhold dose until toxicity is Grade ≤ 1 , or has returned to baseline, then resume treatment at the same dose level or reduce the dose by 1 level at the discretion of the investigator. If recurrent, withhold dose until toxicity is Grade ≤ 1 , or has returned to baseline, then reduce the dose by 1 level.	Withhold dose until toxicity is Grade ≤ 1 , or has returned to baseline, then reduce the dose by 1 level and resume treatment, or discontinue at the discretion of the investigator. If recurrent, permanently discontinue treatment

*Nausea, vomiting, or diarrhea must persist at Grade 3 despite optimal supportive care to require dose modification.

Note: Cycle will not be extended to cover for the missing dose.

Note: For management of GI iRAEs see [Appendix 3 Section 10.3](#).

Note: Participants with confirmed Hy's Law must be discontinued.

Table 10. Dose Modifications for PF-07265028 Related QTcF Prolongation

QTcF >480 ms \leq 500 ms	QTcF >500 ms	Recurrent QTcF >500 ms	QTcF >500 ms or >60 ms change from baseline, and Torsade de pointes or polymorphic ventricular tachycardia or signs/symptoms of serious arrhythmia

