6.5.2. Dose Reductions

No dose reductions are permitted for sasanlimab.

Following dosing interruption or cycle delay due to treatment-related toxicity, the PF-07265028 dose may need to be reduced when treatment is resumed.

No specific dose adjustments are recommended for Grade 1 or 2 treatment-related toxicity. However, investigators should always manage their participants according to their medical judgment based on the particular clinical circumstances.

Participants experiencing recurrent and intolerable treatment-related Grade 2 toxicity may resume dosing at the next lower dose level once recovery to Grade ≤ 1 or baseline is achieved.

Dose reduction of PF-07265028 by 1 and, if needed, 2 dose levels will be allowed depending on the type and severity of toxicity encountered. Participants requiring more than 2 dose reductions will be discontinued from the treatment and entered into the Follow-up phase, unless otherwise agreed between the investigator and the sponsor. All dose modifications/adjustments must be clearly documented in the participant's source notes and CRF.

Once a dose has been reduced for a given participant, all subsequent cycles should be administered at the reduced dose level, unless further dose reduction is required. Intraparticipant dose re-escalation is not allowed.

Participants experiencing a DLT may resume dosing at the next lower dose level (if applicable) once adequate recovery is achieved, and in the opinion of the investigator and sponsor, the participant is benefiting from therapy.

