6.5.3. Dosing Interruptions

Appropriate follow-up assessments should be done until adequate recovery occurs as assessed by the investigator. Criteria required before treatment can resume are described in the Dose Delays ([Section 6.5.4](#)).

Doses may be held up to 4 weeks until toxicity resolution for PF-07265028 and held up to 8 weeks for sasanlimab. Depending on when the AE resolved, a treatment interruption may lead to the participant missing all subsequent planned doses within that same cycle or even to delay the initiation of the subsequent cycle.

If the AE that led to the treatment interruption recovers within the same cycle, then redosing with PF-07265028 in that cycle is allowed. Doses omitted for toxicity are not replaced within the same cycle. The need for a dose reduction at the time of treatment resumption should be based on the criteria defined in the Dose Reductions [Section 6.5.2](#), unless expressly agreed otherwise following discussion between the investigator and the sponsor. If a dose reduction is applied in the same cycle, the participant may need to return to the clinic to receive new drug supply.

In the event of a treatment interruption for reasons other than treatment-related toxicity (eg, elective surgery) lasting >4 weeks, treatment resumption will be decided in consultation with the sponsor.

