6.5.4. Dose Delays

Retreatment following treatment interruption for treatment-related toxicity or at the start of any new cycle may not occur until all of the following parameters have been met:

- ANC $\geq 1,000/\text{mm}^3$.
- Platelets count $\geq 50,000/\text{mm}^3$.
- Hemoglobin ≥ 10 g/dL.
- Nonhematologic toxicities have returned to baseline or Grade ≤ 1 severity (or, at the investigator's discretion, Grade ≤ 2 if not considered a safety risk for the participant).

If a treatment delay results from worsening of hematologic or biochemical parameters, the frequency of relevant blood tests should be increased as clinically indicated.

If these conditions are met within 4 weeks of treatment interruption, PF-07265028 may be resumed. Refer to the Dose Reductions ([Section 6.5.2](#)) for AEs requiring dose reduction at the time of treatment resumption.

If participants require discontinuation of PF-07265028 for more than 4 weeks at any time during the study, then study treatment should be permanently discontinued, unless the investigator's benefit/risk assessment suggests otherwise after discussion with the sponsor. If participants require discontinuation of sasanlimab for more than 8 weeks at any time during the study, then study treatment should be permanently discontinued.

If a treatment interruption continues beyond Day 28 (1 cycle) of the current cycle, then the day when treatment is restarted will be counted as Day 1 of the next cycle.

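### Table 8 restarts Grade 3 hematologic toxicity at the same dose with no exception for Cycle 1 DLTs, for which Section 6.5.2 provides the next lower level

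*Protocol*

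**What the plan says.** Section 6.5 of the Protocol makes Table 8 the working rule for sites: "Toxicities potentially related to PF-07265028 should be managed according to the dose modifications described in Table 8". In that table, the Grade 3 hematologic cell has one outcome. The drug is withheld until the toxicity is Grade 2 or lower or "has returned to baseline, then resume treatment at the same dose level". The cell carries no reduction option, no DLT exception, and no note or pointer to another section.

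Section 6.5.2 has a separate rule for DLTs: "Participants experiencing a DLT may resume dosing at the next lower dose level (if applicable) once adequate recovery is achieved", with the further condition that "in the opinion of the investigator and sponsor, the participant is benefiting from therapy". It also states: "Intraparticipant dose re-escalation is not allowed".

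Two later sections send the reader to 6.5.2. Section 6.5.3 says: "The need for a dose reduction at the time of treatment resumption should be based on the criteria defined in the Dose Reductions" section, "unless expressly agreed otherwise following discussion between the investigator and the sponsor". Section 6.5.4 refers to 6.5.2 "for AEs requiring dose reduction at the time of treatment resumption".

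Section 4.3.3.1 lists the hematologic DLTs, and some of them are met by Grade 3 events. Section 4.3.3 defines DLTs over the first cycle, for the purpose of dose escalation.

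**The concern.** The same event can fall under two restart rules. Table 8 gives the same dose; Section 6.5.2 gives the next lower level, subject to a benefit judgement. A site using the table by itself would return a participant to the dose that had just caused a DLT, in a first-in-human study.

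The cell also differs from its neighbours. The Grade 3 nonhematologic cell of Table 8 and the Grade 3 column of Table 9 (GI toxicity) both allow a one-level reduction, and Section 6.5.2 allows one even for recurrent, intolerable Grade 2 toxicity. The Grade 3 hematologic cell, which covers some DLTs, does not. Tables 9 and 10 carry notes for exceptions and cross-references; Table 8 has none.

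What is at stake is participant safety, not inference.

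**Working it through.** No plan figure is involved, so the check sets the texts side by side.

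**Step 1. Which hematologic DLTs can be Grade 3 events?** The criteria are those of Section 4.3.3.1 as printed. Table 11 equates an ANC below 1000/µL with neutropenia of Grade 3 or higher.

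| # | Criterion (paraphrased) | Region | Can be met at Grade 3? |
|---|---|---|---|
| 1 | Neutropenia above Grade 3, over 7 days | All | No |
| 2 | Febrile neutropenia, ANC below 1000/mm³ | All | Yes, if the ANC is Grade 3 |
| 3 | Neutropenia above Grade 3 with infection | All | No |
| 4 | Grade 3 thrombocytopenia with a bleed of Grade 2 or higher | All | Yes |
| 5 | Grade 3 thrombocytopenia needing transfusion | Japan | Yes |
| 6 | Grade 4 thrombocytopenia | All | No |
| 7 | Grade 4 anemia; in Japan, Grade 3 anemia needing transfusion | All; the Grade 3 clause is Japan only | Japan only |

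In Japan, criteria 2, 4, 5 and 7 qualify: 4 of 7. Elsewhere criterion 5 drops out (7 − 1 = 6) and so does the Grade 3 clause of 7, leaving 2 and 4: 2 of 6. Events of Grade 4 go to the Grade 4 cell, which already reduces or discontinues. These are counts of list items, not of risk.

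**Step 2. Narrow criterion 4 by the worst-toxicity rule.** Section 6.5 bases modification on the worst toxicity when several occur. Treating the bleed as nonhematologic:

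- Grade 2 bleed: the Grade 3 thrombocytopenia is the worst event, so Table 8 gives the same dose. The conflict is clear.
- Grade 3 bleed: the two tie, and the nonhematologic cell brings in the option of one level lower.
- Grade 4 bleed: the nonhematologic Grade 4 cell already requires reduction or discontinuation. No conflict remains.

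**Step 3. How far apart are the restart doses?** From Table 7 (mg QD):

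| Dose at DLT | Table 8 restart | Section 6.5.2 restart | Ratio |
|---|---|---|---|
| 25 | 25 | No lower level listed | – |
| 50 | 50 | 25 | 50/25 = 2.00 |
| 80 | 80 | 50 | 80/50 = 1.60 |
| 125 | 125 | 80 | 125/80 = 1.56 |

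The two rules differ at 3 of 4 provisional levels. The ratios show the spacing of the dose ladder, not the size of any harm.

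**Step 4. Do the retreatment thresholds close the gap?** By Table 11, Grade 3 or higher means ANC below 1000/µL, platelets below 50,000/µL or hemoglobin below 8 g/dL. The Section 6.5.4 minimums for ANC (1,000/mm³) and platelets (50,000/mm³) therefore coincide with the Grade 2 recovery limit in Table 8 and add nothing to it. The hemoglobin minimum (10 g/dL) is stricter and does restrain the Japanese anemia case. None of the three sets a restart dose.

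**Step 5. Does any analysis depend on the restart dose?** No. A participant with a DLT is evaluable whatever share of planned doses was received (Section 4.3.3), the event enters the BLRM at the dose where it occurred, and SAP Section 5.2 summarizes data by initial dose.

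**The case against.** The strongest reply is that Section 6.5, read as a whole, already settles the matter. Sections 6.5.3 and 6.5.4 cover restart within a cycle and after a delay, and both send the reduction decision to 6.5.2, where the specific DLT rule should prevail over a general grade table. This largely stands: the lower level appears to be what was intended. It does not remove the problem, because Table 8 is the instrument that sites are told to follow, and the cell gives an explicit contrary instruction with nothing to prompt a look at 6.5.2.

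Second, 6.5.2 is permissive. A reader might infer that the protocol forbids a same-dose restart after a DLT. It does not: the wording is that dosing may resume lower, if applicable, and 6.5.3 lets investigator and sponsor agree otherwise. The conflict is between a flat same-dose instruction and a conditional lower-dose provision.

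Third, a reader might infer that a literal use of Table 8 bypasses any judgement about continuing treatment. The documents do not support that either. Section 8 requires immediate discussion of safety issues with the sponsor on whether the participant continues, Section 6.3.1 has the sponsor set the dose through the IRT, and SAP Section 6.1.1 has investigators and sponsor agree the final DLT call at the dose level review meeting. These lower the risk. None names a restart dose, and the SAP does not say that the DLT call precedes restart.

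**Conclusion.** The point holds in a narrow form. Table 8 conflicts with Section 6.5.2 only for Cycle 1 DLTs that are Grade 3 hematologic events: febrile neutropenia with a Grade 3 ANC; Grade 3 thrombocytopenia with bleeding, clearly so when the bleed is Grade 2; and, in Japan, Grade 3 thrombocytopenia or anemia requiring transfusion. It should be corrected, but it does not threaten the trial.

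The documents do not say how many participants would be affected. I take the number to be small: the events are few, they must fall in Cycle 1, and DLTs serve Part 1 escalation, which is about 60 of at most 240 participants. The conclusion also assumes that febrile neutropenia is handled in the hematologic row, as Section 4.3.3.1 classifies it, and that bleeding is handled in the nonhematologic row.

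Two wider readings are not supported. The finding does not extend to Grade 3 nonhematologic or GI events, because Tables 8 and 9 already allow a reduction there. Nor does it touch the MTD estimate, sample size, stopping rules or planned analyses.

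**What to change.** Add one sentence to the Grade 3 hematologic cell of Table 8, and to no other cell:

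> If the event is a DLT, follow Section 6.5.2 (next lower dose level, if applicable, after recovery and if investigator and sponsor judge benefit), unless expressly agreed otherwise between investigator and sponsor (Section 6.5.3).

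A general override of Tables 8 and 9 should be avoided, since it would take away the same-level option that now exists for Grade 3 nonhematologic and GI events.

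The change needs no new procedure, visit or participant. Its one drawback is that a participant reduced after such a DLT stays at the lower dose, because Section 6.5.2 bars re-escalation.

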Dose levels that have cleared the DLT period in Part 1 may be expanded up to 10 participants PF-07265028 administered as monotherapy or in combination sasanlimab at or below the MTD. Expansion of dose levels will be based on evolving clinical data (including safety, PK, and PD) to explore activity and help identify the RDE of the monotherapy and/or combination in Part 2.

Please see below for intra-participant dose escalation rules and rules for crossover from Part 1A to Part 1B.

- To minimize the risk that an individual participant may be exposed to a sub-therapeutic dose, intra-participant dose escalation of PF-07265028 in Part 1 to the maximal dose level that has previously been determined to be safe (based on BLRM) may be allowed if the protocol required safety assessments for the previous treatment cycle have been performed and as follows:
 1. Participant has completed 2 cycles of treatment at the current dose level; or if disease progression occurs.
 2. No Grade ≥ 3 treatment-emergent toxicities were experienced at the participant's current dose level.
 3. If a clinical rationale is provided by the investigator and approved by the sponsor.
- In Part 1A (monotherapy dose escalation) participants with SD after 2 cycles of treatment, and additionally participants with a RECIST response of PR or CR, who then experience PD, may rollover to the combination cohort regardless of prior PDx status.

Participants in Part 1 must have recently obtained archival tumor tissue available (collected within 6 months prior to screening). If the archival sample is older than 6 months, the participant must consent to undergo a fresh pre-treatment biopsy during the screening period. If a new biopsy represents a significant safety risk in the opinion of the investigator, the participant may be considered for enrollment with archival samples only after discussion with the sponsor.

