10. Active inflammatory GI disease, known diverticular disease or previous lap-band surgery. Impairment of GI function or GI disease that may significantly alter the absorption of PF-07265028, such as history of GI surgery with may result in intestinal blind loops and participants with clinically significant gastroparesis, short bowel syndrome, unresolved nausea, vomiting, active inflammatory bowel disease or diarrhea of NCI CTCAE Grade > 1 . Proton-pump inhibitors are not allowed at least 7 days prior to C1D1 and throughout the study.
11. Hypertension that cannot be controlled by medications ($> 150/90$ mm Hg despite optimal medical therapy).

12. Any of the following in the previous 6 months: myocardial infarction, congenital long QT syndrome, Torsades de pointes, arrhythmias (including sustained ventricular tachyarrhythmia and ventricular fibrillation), right bundle branch block and left anterior hemiblock (bifascicular block), unstable angina, coronary/peripheral artery bypass graft, symptomatic congestive heart failure (New York Heart Association class III or IV), cerebrovascular accident, transient ischemic attack, or symptomatic pulmonary embolism; DVT; arterial occlusive disease; ongoing cardiac dysrhythmias of NCI CTCAE Grade ≥ 2 , atrial fibrillation of any grade that is uncontrolled, or QTcF interval >470 ms at screening.
13. Known or suspected hypersensitivity to active ingredient/excipients of study treatments.
14. Other medical or psychiatric condition including recent (within the past year) or active suicidal ideation/behavior or laboratory abnormality that may increase the risk of study participation or, in the investigator's judgment, make the participant inappropriate for the study .

Exceptions:

- Limited, focal radiation therapy (including Gamma-Knife) require only a 3-day period before study entry and the absence of any radiation-induced complications.
- Palliative radiation therapy within 14 days of study entry (2 weeks in the case of immunotherapy) and the absence of any radiation-induced complications.

Prior/Concomitant Therapy:

15. Prior administration of HPK1 inhibitor.
16. Prior systemic anti-cancer therapy within 14 days (6 weeks for mitomycin C or nitrosoureas) prior to study treatment. Participant with prostate cancer are permitted to continue on LHRH agonists/antagonists.

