6.3. Measures to Minimize Bias: Randomization and Blinding

6.3.1. Allocation to Study Intervention

This is an open-label Phase 1 study that will not be randomized. The investigator's knowledge of the treatment should not influence the decision to enroll a particular participant or affect the order in which participants are enrolled.

No participant will receive study intervention until the investigator or designee has received the following information in writing from the sponsor:

- Confirmation of the participant's enrollment;
- Specification of the dose level for that participant and;
- Permission to proceed with dosing the participant.

Study intervention will be dispensed at the study visits summarized in the [SoA Table 1](#).

Returned study intervention must not be redispensed to the participant.

Allocation of participants to treatment groups will proceed through sponsor or designee and will include the participant number and randomization number. The site staff will e-mail a complete Registration Form to the designated sponsor study team member or designee. The sponsor will assign a participant identification number and supply this number to the site. The form must be stored in the site's files. The participant identification number will be used on all study-related documentation at the site.

Returned study intervention must not be re-dispensed to the participants.

This is an open-label study; the study intervention dose will be determined by the sponsor and dispensed to the participant using an IRT. The IRT will assign a kit number for study intervention administration for each participant.

The study-specific IRT reference manual and IP manual will provide the contact information and further details on the use of the IRT system.

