Reduce the dose of drug by one level without interruption of dosing. Following dose reduction, the drug dose may be resumed at the previous level in the next cycle if the QTcF has decreased to within 30 ms of baseline or <450 ms but subject must be monitored closely for QT prolongation for the first cycle at the increased dose.	Withhold dose for up to 14 days. If QTcF returns to within 30 ms of baseline or <450 ms within 14 days, resume and reduce by 1 dose level.	Permanently discontinue treatment if QTcF >500 ms recurs despite appropriate dose reduction and correction/elimination of other risk factors (eg, serum electrolyte abnormalities, concomitant QT prolonging medication)	Permanently discontinue treatment

Note: For all episodes of QTc prolongation, regardless of grade, check electrolyte (potassium, calcium, and magnesium) levels and correct any abnormalities. If possible, stop any medications that may prolong the QT interval (see [Section 8.2.4](#) for management of QTc prolongation).

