8.2.4. Electrocardiograms

Standard 12-lead ECGs utilizing limb leads (with a 10 second rhythm strip) should be collected at times specified in the [SoA](#) section of this protocol using an ECG machine that automatically calculates the heart rate and measures PR, QT, and QTc intervals and QRS complex. All 12 lead ECGs should be confirmed by a qualified individual at the institution or use a fully validated automated ECG analysis. All ECGs in a single participant should be analyzed by the same reader. Alternative lead placement methodology using torso leads (eg, Mason-Likar) should not be used given the potential risk of discrepancies with ECGs acquired using standard limb lead placement. All scheduled ECGs should be performed after the participant has rested quietly for at least 10 minutes in recumbent or semi-recumbent position and before blood draws or vital signs.

At each time point (see [SoA](#)) except screening and EOT, 3 consecutive ECGs (ie, triplicate ECGs) will be performed at approximately 2 minutes apart to determine the mean QTcF interval. ECG assessments should precede blood collection for clinical laboratory tests. When coinciding with blood sample draws for PK, plan the timing of ECG well so that the PK collection afterwards can be around the intended time.

If a) a postdose QTcF interval remains ≥ 60 ms from the baseline **and** is >450 ms; or b) an absolute QT value is ≥ 500 ms for any scheduled ECG for greater than 4 hours (or sooner, at the discretion of the investigator); or c) QTcF intervals get progressively longer, the participant should undergo continuous ECG monitoring until QTcF values from 2 successive ECGs fall below the threshold value that triggered the repeat measurement. In addition, if verified QTcF values continue to exceed the criteria above, immediate correction for reversible causes including electrolyte abnormalities, hypoxia and concomitant medications for drugs with the potential to prolong the QTcF interval should be performed.

A cardiologist should be consulted if QTcF intervals do not return to less than the criteria listed above after 8 hours of monitoring (or sooner, at the discretion of the investigator). If in that timeframe the QTcF intervals rise above the threshold values, the study intervention will be held until the QTcF interval decreases to below the threshold values. Participants may resume study intervention at the current dose level or next lower dose level after discussion

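### Protocol Table 10 lets a PF-07265028 dose reduced for QTcF above 480 and up to 500 ms go back up in the next cycle, while Section 6.5.2 bars that increase and names no exception

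*Protocol*

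**What the plan says.** Two places in the protocol govern what happens after a QTcF-driven reduction of PF-07265028.

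- **Section 6.5, Table 10, first column (QTcF above 480, up to 500 ms).** The action is "Reduce the dose of drug by one level without interruption of dosing". The dose may then be "resumed at the previous level in the next cycle if the QTcF has decreased to within 30 ms of baseline or <450 ms". The table treats this as a dose increase and asks for close QT monitoring during the first cycle at the higher dose.
- **Section 6.5.2, Dose Reductions.** After a reduction, "all subsequent cycles should be administered at the reduced dose level"; the only exception named is a further reduction. It adds: "Intraparticipant dose re-escalation is not allowed".

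Three other provisions bear on the point. Exclusion criterion 12 (Section 5.2) rules out a participant with a "or QTcF interval >470 ms at screening", so a screening value of 470 ms is eligible. Protocol Section 9.3.5.1 and SAP Section 6.1.5 define the baseline ECG as the last one before Cycle 1 Day 1 dosing. Section 6.5.4 bars treatment at the start of a new cycle until nonhematologic toxicity is back to baseline or Grade 1 or lower; Grade 2 is acceptable at the investigator's discretion if it is not judged a safety risk.

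**The concern.** The same act, giving the previous higher dose in the cycle after a QTcF reduction, is allowed by one section and forbidden by another. A site that follows Table 10 breaches Section 6.5.2; a site that follows Section 6.5.2 withholds a dose that Table 10 allows. At stake is whether exposure rises again after QTcF prolongation in a first-in-human trial.

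The return test raises a second, smaller question. One limb is relative to baseline, whereas the reduction trigger is absolute. If baseline is high enough, a single reading can satisfy the test for going up and also lie in the range where the column says to go down.

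**Working it through.** **Step 1. Does any other text reconcile Table 10 and Section 6.5.2?**

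- Section 4.1.1 has an intra-participant escalation rule, but it covers Part 1 only and its first condition is "Participant has completed 2 cycles of treatment at the current dose level; or if disease progression occurs". That is not a next-cycle return after toxicity.
- Sections 6.5.2 and 6.5.3 allow for sponsor agreement, but on other matters: going beyond two reductions, and whether a reduction is needed when treatment resumes.
- Section 8.2.4 says "Participants may resume study intervention at the current dose level or next lower dose level after discussion" with the sponsor. That applies after a hold. The first column of Table 10 has no hold, so this text does not settle the question.
- Table 10 does not cite Section 6.5.2, and Section 6.5.2 does not cite Table 10.

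Nothing reconciles them. This result does not depend on baseline.

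**Step 2. Can the return test be passed above 480 ms?**

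Inputs: reduction range 481 to 500 ms and return test (Table 10); screening limit 470 ms (Section 5.2). Whole milliseconds are used, and baseline *b* is taken equal to the screening value, which is an assumption.

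The limb requiring QTcF below 450 ms cannot be met above 480 ms, so only the comparison with baseline matters. The highest QTcF that passes it is:

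- *b* + 30, if exactly 30 ms counts as within 30 ms;
- *b* + 29, if the difference must be less than 30 ms.

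The test can be passed above 480 ms when *b* + 30 > 480, so *b* ≥ 451, or when *b* + 29 > 480, so *b* ≥ 452.

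| Baseline (ms) | QTcF values that pass the return test and also call for a reduction (≤30 reading) | Same (<30 reading) |
|---|---|---|
| 450 or lower | none | none |
| 455 | 481–485 | 481–484 |
| 460 | 481–490 | 481–489 |
| 465 | 481–495 | 481–494 |

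**Step 3. Does the wording about a decrease change this?**

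The text could mean that the value must first have been outside the window. At baseline 470 ms under the ≤30 reading, the window reaches 500 ms, so no first-column value lies outside it and that baseline drops out. The ranges are then:

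- ≤30, any decrease: 451–470 ms;
- ≤30, outside the window first: 451–469 ms;
- <30, with or without that requirement: 452–470 ms.

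Baselines of 452–469 ms are common to all readings.

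**Example valid under every reading.** Baseline 465 ms; dose reduced at 498 ms (498 − 465 = 33, outside the window); next reading 490 ms (490 − 465 = 25, inside it). The return test is passed, yet 490 ms is above 480 ms.

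**The case against.** The best defence is that Table 10 is a specific exception. Section 6.5.2 introduces reductions as following a dosing interruption or a cycle delay, whereas the first column reduces without interrupting. Table 10 describes the return expressly and attaches its own monitoring, so the return looks deliberate. The summary of changes lists the QTcF table among the additions, which would make it the later as well as the more specific text. This is a plausible account of intent. It does not settle the matter, because the Section 6.5.2 rule applies once a dose has been reduced, without qualification, and neither section states an exception.

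On the secondary point, the reduction is an instruction and the return only a permission, so many readers would let the instruction prevail; Table 10 does not say so. Section 6.5.4 also applies directly, since the return occurs at a new cycle. It limits the return, but it leaves discretion at Grade 2 and gives no QTcF value. The documents do not map CTCAE grades to milliseconds, so it cannot be shown to exclude the 490 ms example. If Section 6.5.2 governs, the secondary point disappears.

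Other safeguards are real. Section 6.3.1 states that "the study intervention dose will be determined by the sponsor and dispensed to the participant using an IRT"; Section 8.2.4 stops treatment at QTcF above 515 ms or if symptoms appear; the monkey telemetry study in Section 2.2.7 found no QT change. They lower the risk, but the sponsor setting the dose still faces the same two rules.

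Three stronger readings are not supported:

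- A reader might infer that the protocol generally sends participants back to a higher dose above 480 ms. The return is optional, and there is no overlap at baselines of 450 ms or lower.
- A reader might infer that DLT or MTD data are affected. The return comes in the next cycle, after the Cycle 1 DLT window.
- A reader might see the Grade 2 discretion in Section 6.5.4 as contradicting the recovery rules in Tables 8 and 9. It sets conditions that must be met before retreatment, so holding to the stricter recovery level satisfies both.

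**Conclusion.** The main point stands as an internal inconsistency in the protocol: the same dose increase is both permitted and prohibited. It reaches every participant reduced under the first column of Table 10, at any baseline. It should be corrected; the likely cause is an exception that was intended but never written, not a deliberate choice between two safety policies.

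The secondary point stands in limited form. For baselines above 450 ms the return test can be met at a QTcF for which the same column instructs a reduction, subject to the Section 6.5.4 conditions. The range of 452–469 ms assumes whole milliseconds and a baseline equal to the screening value. Baseline is in fact the last pre-dose ECG, so it can differ from screening and could slightly exceed 470 ms. With averaged triplicates under the ≤30 reading, any baseline above 450 ms qualifies.

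No participant count or percentage follows, because the documents give no frequency for QTcF prolongation or for baselines above 450 ms.

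**What to change.** Choose one rule.

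- **Option A.** Delete the return sentence from the first column of Table 10. Section 6.5.2 then governs and both points are resolved. Cost: one sentence.
- **Option B.** Add *except as stated in Table 10* to Section 6.5.2, and in the first column require QTcF of 480 ms or less in addition to the existing return test. Cost: one line in each place.

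Option B has a small downside. The permitted distance from baseline becomes the smaller of 30 ms and 480 minus baseline: 30 ms at 450, 25 at 455, 20 at 460, 15 at 465 and 10 at 470. Participants with a baseline above 450 ms must therefore come closer to baseline before the higher dose returns. Baselines up to 450 ms are unaffected.

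Neither option adds assessments. The column for QTcF above 500 ms can stay, because its restart is already one level lower and does not conflict with Section 6.5.2. No change to Section 6.5.4 is needed.
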